# 7.6 Interim Analyses

An interim database lock may be performed to support a regulatory filing, if needed. The treatment assignments will be unblinded to selected individuals for interim analyses. Unblinded data will be disseminated only to Allergan personnel who are directly involved in submission-related activities. These data will remain blinded for all Allergan personnel who are directly involved with the ongoing operational activities of the clinical study, all subjects,

and all site personnel until the final database lock. Further details regarding an interim analysis will be provided in the analysis plan.

## 7.7 Final Analyses

A final database lock will be performed following the last subject's completion of the day 360 (study exit or early discontinuation) visit. All study data, from every subject and every visit, will be included in this final analysis.

## 8 Study Visit Schedule and Procedures

Please see Table 1 for a schematic of the schedule of visits and procedures.

### 8.1 Subject Entry Procedures

## 8.1.1 Overview of Entry Procedures

Prospective subjects as defined by the criteria in Sections 4.3 and 4.4 (inclusion and exclusion criteria, respectively) will be considered for entry into this study.

## 8.1.2 Informed Consent and Subject Privacy

The study will be discussed with the subject, and a subject wishing to participate must give informed consent prior to any study-related procedures or change in treatment. The subject must also give authorization and other written documentation in accordance with the relevant country and local privacy requirements (where applicable) prior to any study-related procedures or change in treatment.

Each subject that provides informed consent will be assigned a subject number that will be used on subject documentation throughout the study.

#### 8.2 Washout Intervals/Run-in

Subjects taking prohibited medications, agents that could interfere with neuromuscular transmission, or muscle relaxants must undergo a washout of the medication(s) for at least 28 days prior to entering the study. If washout is required for the purposes of this study then the subject must sign the informed consent before the washout is commenced.

For subjects who have undergone facial shaping procedures (eg, use of fat-reducing injectables or skin-tightening laser treatments; implantation of a prosthetic device or autologous fat transplantation; use of temporary, semi-permanent, or permanent filler product in the face) prior to screening, the procedure must have occurred at least 6 months prior to entering the study.

# 8.3 Procedures for Final Study Entry

A subject is considered to have enrolled in the study upon randomization to treatment on day 1 after completion of all pre-treatment and randomization procedures and after the investigator re-verifies the subject has met all the inclusion and exclusion criteria for study

See Section 5.5 for the method for assignment to treatment groups/randomization.

#### 8.4 Visits and Associated Procedures

#### **Training**

The investigator performing MMPS and LFSC assessments will be trained on the appropriate use of the MMPS and LFSC prior to screening study subjects. Documentation of investigator training will be maintained in the study center regulatory binder with a copy sent to Allergan.

On day 1, enrolled subjects will view a training presentation on how to use the LFSC to assess their own lower facial shape. Each subject will choose the lower facial shape grade that best matches the contour of the lower portion of his/her face (1, 2, 3, or 4).

#### Screening, Treatment, and Follow-up Visits

For a summary of the procedures to be performed at scheduled visits, see Table 1 (Schedule of Visits and Procedures).

Evaluations should be performed by the same evaluator throughout the study whenever possible. If it is not possible to use the same evaluator to follow the subject, then evaluations should overlap (examine the subject together and discuss findings) for at least 1 visit.

## 8.5 Instructions for the Subjects

#### 8.6 Unscheduled Visits

Unscheduled visits can be performed if safety concerns arise and at the discretion of the investigator. If a subject is seen for an unscheduled visit, an assessment and record of

adverse events should be completed. Additional evaluations should be performed, as necessary, and the appropriate case report forms should be completed.

## 8.7 Compliance with Protocol

Enrolled subjects should be able to attend all clinic visits for treatment administration and followup.

## 8.8 Early Discontinuation of Subjects

Subjects may voluntarily withdraw from the study at any time. Notification of early subject discontinuation from the study and the reason for discontinuation will be made to Allergan and will be clearly documented on the appropriate case report form. All day 360/study exit procedures should be performed (Table 1), including an exit CT scan, unless the investigator proposes a medical reason to waive the exit CT scan.

#### 8.9 Withdrawal Criteria

Subjects should be discontinued from the study if any of the following criteria are met.

- Subject develops (or has an exacerbation of) any medical condition that, in the opinion of the investigator, would put the subject at an unacceptable medical risk or compromises the subject's ability to participate in the study.
- Subject is unable/unwilling to comply with study procedures.

Where possible, the decision to withdraw a subject from the study should be discussed with Allergan.

## 8.10 Study Termination

The study may be stopped at his/her study site at any time by the site investigator. Allergan may stop the study (and/or the study site) for any reason with appropriate notification.

#### **9** Adverse Events

Adverse events occurring during the study will be recorded on an adverse event case report form. If adverse events occur, the first concern will be the safety of the study participants.

#### 9.1 **Definitions**

#### 9.1.1 Adverse Event

An adverse event is any untoward medical occurrence in a patient or clinical investigation subject administered a pharmaceutical product and that does not necessarily have a causal relationship with this treatment. An adverse event can therefore be any unfavorable and unintended sign (including an abnormal laboratory finding), symptom, or disease temporally associated with the use of a medicinal (investigational) product, whether or not related to the medicinal (investigational) product. In addition, during the screening period, adverse events will be assessed regardless of the administration of a pharmaceutical product.

Note: Adverse events must be collected once informed consent has been obtained, regardless of whether or not the subject has been administered study drug.

Progression of treatment indication including new or worsening of anticipated clinical signs or symptoms, which are collected as clinical efficacy variables and assessed as unequivocally associated with the disease progression and/or lack of efficacy, should NOT be reported as adverse events unless the disease progression is greater than anticipated in the natural course of the disease.

Adverse events will be assessed, documented, and recorded in the case report forms throughout the study (ie, after informed consent has been obtained). At each visit, the investigator will begin by querying for adverse events by asking each subject a general, non-directed question such as "How have you been feeling since the last visit?" Directed questioning and examination will then be done as appropriate. All reported adverse events will be documented on the appropriate case report form.

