# 1.3 Rationale for Safety Assessments, CT Imaging, and Dental Examination

Safety assessments include attention to potential local and systemic effects of BOTOX treatment of MMH. Local adverse events (eg, pain, discomfort, and muscle ache at sites of injection) have been reported within the first 2 weeks posttreatment; therefore, a telephone follow-up visit is scheduled approximately 14 days following the day 1 and day 180 treatments. Because the masseter muscle is 1 of the primary muscles of mastication, masticatory difficulties (eg, transient masseter muscle fatigue after vigorous chewing and weakness on chewing) have been reported. Temporary speech disturbances have also been reported. In general, these adverse events have been reported as mild and resolved without treatment.

In the literature, nonclinical studies have reported on mandibular bone and dental changes following BOTOX treatment of the masseter muscle in animal models (Navarrete et al, 2013; Rafferty et al, 2012; Tsai and Huang, 2008; Tsai et al, 2010). However, differences in the structure and function of the mandible and dentition in animals contribute to difficulty interpreting the relevance to humans (refer to the Investigator's Brochure). One clinical study of botulinum toxin (Dysport®) injected in the masseter muscles of 10 women showed no changes in mandibular cortex thickness, mandibular bone thickness, and mandibular

volume on CT at 3 months (Chang et al, 2011). It is unknown whether BOTOX treatment of MMH may impact characteristics of the mandible and/or dentition in subjects. The medical literature does not indicate any clinically relevant change to these craniofacial structures adjacent to the masseter muscle. Therefore, Allergan has developed exploratory CT measures to determine whether any potential safety and/or efficacy signals may be detected that are not currently reported in the medical literature.

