#### 5.10 Retreatment

[figure not shown]
After treatment on day 1, subjects will receive a second treatment based on meeting the following criteria at the day 180 visit:

- Allergan decision and written notification to study sites allowing a second treatment
- Subject has presence of bilateral masseter muscle hypertrophy of at least marked (grade 4), as measured by the investigator using the MMPS.
- Females of childbearing potential must have a negative urine pregnancy test prior to treatment.

The second treatment is only allowed at the day 180 visit. Retreatment is prepared and administered in the same manner as described in Sections 5.1 to 5.9. Subjects will receive the same treatment at day 180 as they received at day 1.

- **6** Response Measures and Summary of Data Collection Methods
- **6.1** Efficacy Measures
- 6.2 Primary Efficacy Measure
- lower facial volume (cm³) calculated from VECTRA M3 digital photography system 3D image models (see Attachment 12.1.2)
- 6.3 Secondary Efficacy Measure
- investigator's assessment of MMH using the MMPS (5 grades: 1 = minimal, 2 = mild, 3 = moderate, 4 = marked, 5 = very marked; see Attachment 12.1.1)

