#### 12 Attachments

# 12.1 Examination Procedures, Tests, Equipment, and Techniques

## **12.1.1** Masseter Muscle Prominence Scale (MMPS)

#### Instructions

Using visual inspection and palpation, you will rate the masseter muscle prominence during rest and function, by separately evaluating the right and left side of the subject's face.

- Sit directly in front of the subject and inspect the contour of the face in the clenched and unclenched state.
- Define the posterior and anterior border of each masseter, as well as the superior and inferior margins.
- While the subject clenches and relaxes, use your fingers to feel the dimensions and surface texture of each masseter.
- Have the subject repeat the sequence of clenching and relaxing at least twice. As best as possible, distinguish masseter muscle from bone and other non-muscular soft tissue (eg, fat).
- Rate each masseter separately, and record your ratings. In the presence of discordant
  assessment between rest and clenched states, the subject's masseter prominence
  assessment noted in the clenched state should factor most significantly in determining the
  overall rating for each side of the face.

Rating	Clinical Evaluation		
Minimal (1)	AT REST: With mouth closed and no clenching, surface overlying masseter is concave. There is no contour contributed by masseter muscle. Masseter is not palpable.  AT CLENCH: No visible difference in contour compared with when mouth is closed, no clenching. Masseter is minimally palpable and difficult to define.		
Mild (2)	AT REST: With mouth closed and no clenching, surface overlying masseter is flat or slightly concave. The contour contributed by masseter muscle may or may not be visible. Masseter is minimally palpable.  AT CLENCH: With clenching, minimal difference in lower facial contour compared with when mouth is closed, no clenching. Portion of masseter bulk may be visible and palpable.		
Moderate (3)	AT REST: With mouth closed and no clenching, surface overlying masseter is flat or convex. The contour contributed by masseter muscle may or may not be visible.  Masseter is palpable.  AT CLENCH: With clenching, the lower face is more convex in contour compared with when mouth is closed, no clenching. Masseter bulk is easily identifiable, palpable, and firm.		

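### At post-treatment visits nothing puts the investigator's MMPS grade before the adverse event question, so a same-visit report of chewing weakness can reach the grader first

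*Protocol*

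**What the plan says.** Protocol Section 9.1.1 states that "At each visit, the investigator will begin by querying for adverse events by asking each subject a general, non-directed question", and continues: "Directed questioning and examination will then be done as appropriate".

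The same role grades the MMPS. Section 6.3 defines the secondary measure as the "investigator's assessment of MMH using the MMPS". Section 5.10 uses the same grade as a day 180 retreatment criterion: "Subject has presence of bilateral masseter muscle hypertrophy of at least marked (grade 4), as measured by the investigator using the MMPS". The training paragraph of Section 8.4 also gives the rating to this role: "The investigator performing MMPS and LFSC assessments will be trained on the appropriate use of the MMPS and LFSC prior to screening study subjects". The next paragraph adds that "Evaluations should be performed by the same evaluator throughout the study whenever possible".

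The scale is a judgement made by hand and eye. Attachment 12.1.1 begins: "Using visual inspection and palpation, you will rate the masseter muscle prominence during rest and function". Where rest and clench disagree, the clenched state carries most weight.

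Section 1.3 notes that "masticatory difficulties (eg, transient masseter muscle fatigue after vigorous chewing and weakness on chewing) have been reported". Section 1 says such events typically appear within 2 weeks of treatment and resolve within 1 to 3 months.

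Protocol 7.3.2 and SAP 5.3 define a responder as MMPS grade 3 or lower. The masking text in Protocol 5.3 covers vials, cartons, the drug reconstitutor and injection volume. It does not address what the grader learns after injection.

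**The concern.** Chewing weakness is a recognised effect of the treatment, so hearing of it tells the grader something about the assignment. It also concerns the function of the muscle that the grader is about to feel at clench. If the adverse event question comes first, this information arrives just before a subjective grade in which the step between 4 and 3 separates non-response from response.

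The cue is expected mainly on BOTOX and points towards a lower grade, so any influence would tend to widen the responder difference in favour of BOTOX. What is at stake is the credibility of the secondary endpoint, including the efficacy data through day 90 that the Data Review Committee sees (Protocol 3.1).

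**Working it through.** **1. The passages side by side.** Section 9.1.1 gives the adverse event question to the investigator, at the start of each visit. Sections 6.3, 5.10 and 8.4 give the MMPS to the investigator. Section 8.4 prefers one evaluator throughout. The readable text contains no separate MMPS rater, no rule that grading comes first, and no rule that keeps adverse event reports from the grader. The match is by role, not by person: a site could split the tasks, but nothing requires it.

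**2. Which visits count.** Day 1 grading precedes treatment, and days 14 and 194 are telephone contacts. The issue is therefore confined to post-treatment clinic visits. With onset typically within 2 weeks and resolution in 1 to 3 months, a fresh cue is most likely at days 30 to 90.

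**3. The plan's own figure.** The only power figure is 93% in Protocol 7.5, for lower facial volume (40 versus 10 subjects, effect size 1, 1-sided 0.10). It reproduces: a noncentral t with 48 degrees of freedom and noncentrality 1/√(1/40 + 1/10) = 2.83 gives 93.6%. It does not bear on the MMPS, for which the documents give no planning figure.

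**4. How informative the cue is.** Allocation of 40:10 gives a starting probability of BOTOX of 40/50 = 0.80. Let a and b be the shares of BOTOX and placebo subjects who report chewing weakness. Both are assumed. Then P(BOTOX | report) = 0.8a / (0.8a + 0.2b):

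- a = 0.10, b = 0.05: 0.080/0.090 = 0.889
- a = 0.20, b = 0.03: 0.160/0.166 = 0.964
- a = 0.40, b = 0.01: 0.320/0.322 = 0.994

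**5. What it could do to the responder comparison.** Suppose there is no true effect and the responder rate is p0 in both arms. A share f of BOTOX subjects, and none on placebo, report chewing weakness. A share s of the non-responders among them are graded 3 or lower because of it. The spurious difference is (1 − p0) × f × s. The rejection probability comes from exact enumeration of an unstratified Mantel-Haenszel chi-square, 40 BOTOX versus 40 pooled placebo (4 × 10, SAP Section 5), at 2-sided 0.05 (SAP 2.3.7).

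| p0 | f | s | Difference | Rejection probability |
|---|---|---|---|---|
| 0.1 to 0.3 | any | 0 | 0 | 0.048 to 0.059 |
| 0.3 | 0.1 | 0.25 | 0.7 × 0.1 × 0.25 = 1.8 points | 0.051 |
| 0.2 | 0.2 | 0.5 | 0.8 × 0.2 × 0.5 = 8.0 points | 0.133 |
| 0.1 | 0.3 | 0.5 | 0.9 × 0.3 × 0.5 = 13.5 points | 0.376 |

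The second and last rows are the extremes over p0 0.1 to 0.3, f 0.1 to 0.3 and s 0.25 to 0.5. The documents give none of these three inputs.

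**6. What the figures cover.** They count all knowledge of chewing weakness, whenever it was gained. If a share k of it is heard only at the visit in question, the part that reordering removes is k times the difference. In the middle case that lies anywhere from 0 to 8 points, and nothing in the documents fixes k.

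**7. The scoring rule.** SAP 2.3.5 averages the two sides and rounds half grades up. A 4/4 subject graded 3/4 scores 3.5, which becomes 4, still a non-responder. Only 3/3 gives 3. A false responder from 4/4 therefore needs both sides lowered, which argues against large values of s.

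**The case against.** **The sentence may not set a visit order.** It stands among the adverse event definitions and can be read as a rule of elicitation: open question first, directed questions after. It does not mention the MMPS. Section 8 refers to Table 1 for visit procedures, and that table is not in the supplied text. A reader might infer that the protocol requires adverse events before the MMPS. The documents do not go that far. What remains is that, on either reading, no readable text puts the MMPS first, and the plain wording invites the opposite.

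**The grader meets the effect anyway.** The MMPS involves repeated clenching, and its upper grades are partly defined by firmness, so a weakened muscle is felt directly. The same evaluator may also remember earlier reports. Both points stand and limit what reordering can gain.

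**The illustration may be too high.** It treats chewing weakness and true response as independent. Subjects with weakened masseters may more often be true responders, which would leave fewer grades to distort. This also stands.

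**Retreatment.** A reader might infer that the cue materially affects who is reinjected at day 180. The protocol's own timing speaks against that: the typical event has resolved by then, so the influence would come mainly from memory.

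**Safety first.** Opening with adverse events fits the priority given to safety in Section 9. Any reordering should therefore yield to an urgent concern.

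**Conclusion.** The point holds as a cheap improvement. At post-treatment clinic visits, mainly days 30 to 90, the grader can hear of chewing weakness just before giving the subjective grade that decides MMPS response, and nothing readable prevents it.

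The likely direction is an inflated responder difference. The size is unknown. The 1.8 to 13.5 points above rest wholly on assumed inputs and are a ceiling for the same-visit part under those inputs, not an estimate of it. A reader might also infer that grades are distorted in BOTOX subjects only. The documents give no rate in either arm, so mainly BOTOX subjects is as far as one can go.

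The primary endpoint is calculated from 3D images with technician-verified landmarks (Attachment 12.1.2), so this route does not reach it directly. An effect on day 180 retreatment is probably small.

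**What to change.** Reword Section 9.1.1 and align the visit schedule. At each post-treatment clinic visit the investigator should grade the MMPS and LFSC, and lock them in the eCRF, before asking the general adverse event question and without reviewing the adverse event log. The exception is a subject who raises an urgent safety concern. If Table 1 already sets an order, the two texts should be made to agree.

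The cost is a change in the order of procedures and in site training, with no added staff, visit or procedure. Adverse event collection stays complete, and the question comes a few minutes later. The fix is partial, because the evaluator may remember events from the day 14 call or earlier visits.

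It should not be extended to delaying the causality review of events reported in the telephone calls. From day 14 to day 30 that would be a nominal 30 − 14 = 16 days, and reporting under Section 9.2 depends on that review.

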#### 9.1.2 Serious Adverse Event

A serious adverse event is any adverse event occurring at any dose that results in any of the following outcomes: death, a life-threatening adverse event, inpatient hospitalization or prolongation of existing hospitalization, a persistent or significant disability/incapacity, or a congenital anomaly/birth defect. Important medical events that may not result in death, be life-threatening, or require hospitalization may be considered a serious adverse event when, based upon appropriate medical judgment, they may jeopardize the patient or subject and may require medical or surgical intervention to prevent one of the outcomes listed in this definition. (See Section 9.3 for procedures for reporting a serious adverse event.)

Allergan considers all cancer adverse events as serious adverse events. In addition, Allergan considers any abortion (spontaneous or nonspontaneous) as a serious adverse event.

Pre-planned surgeries or procedures for pre-existing, known medical conditions for which a subject requires hospitalization is not reportable as a serious adverse event.

Any pre-planned surgery or procedure should be clearly documented in the site source documents by the medically qualified investigator at the time of the subject's entry into the study. If it has not been documented at the time of the subject's entry into the study, then it should be documented as a serious adverse event and reported to Allergan.

## 9.1.3 Severity

A clinical determination will be made of the intensity of an adverse event. The severity assessment for a clinical adverse event must be completed using the following definitions as guidelines:

Mild Awareness of sign or symptom, but easily tolerated.

Moderate Discomfort enough to cause interference with usual activity.

Severe Incapacitating with inability to work or do usual activity.

Not applicable In some cases, an adverse event may be an 'all or nothing' finding that

cannot be graded.

